13, 2020) due to the coronavirus pandemic, home visits have been converted to audiovisual visits. The PT will provide resources to obtain low cost equipment (e.g., walkers), if required. In both groups, acute need for PT/OT services will be as per standard of care (i.e., physician referral); study participation (in either randomized group) will not impact standard care. The OT will then assist the patient in identifying valued activities (i.e., activities performed for their intrinsic worth) in the participant's life. The OT will guide and facilitate developing goals for completing valued activities, based on ratings of importance and satisfaction with performance on the COPM and performed in the participant's home, by the end of the first week. The OT will then evaluate the participant's ability to perform the prioritized activities. The OT will work with the participant to set BA goals for these selected activities, by embedding physical exercise (as recommended by PT) into valued daily routines. Goals will be divided into step-by-step plans, which incorporate appropriate expectations for participant activity during recovery. If the necessary steps to achieve these goals are not readily apparent to the participant, the OT will implement standard problem-solving strategies.^{16,83,85} The visit will end with the OT entering the identified goals for the valued activities into the participant's Progress Worksheet (see below).

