8. Risks

a. Medical risks, listing all procedures, their major and minor risks and expected frequency.

1) Depression: Participants will be asked questions about depression using the PHQ-8, HADS and the SCID. While asking questions, we may detect that the patient has worsening depressive symptoms.

2) Breach of confidentiality: We will be collecting data about the participant, and hence, there is a risk of breach of confidentiality.

b. Steps taken to minimize the risks.

[figure not shown]
Depression (PHQ-8, HADS and SCID): All potential participants who have worsening depression symptoms will be informed that they may be depressed and advised to consult with their health care provider.

If there is any potential concern regarding safety of a participant, a physician on our study team will become involved. The research assistant will be instructed to take the steps outlined in Figure 2 below.

- Complete a Serious Adverse Event Report (SAE) form documenting the outcome of this questionnaire and subsequent action taken.
- If unsure about the patient's risk, contact a study physician to notify them immediately and discuss action to take.

Figure 2. Suicide Risk Management Protocol

Suicide Risk Management Protocol for BA-R Pilot Study

Adapted from Suicide Risk Management Protocol in Post-Cardiac Arrest Survivors: Development, Feasibility, and Outcomes by RA Bucy et al Ann Am Thorac Soc. 2016 Dec 16; Article in Press)

*Suicide prevention helpline by state:

State Number	Local County/City wise
Maryland [name] http://www.suicide.org/hotlines/maryland-suicide-hotlines.html	
 • Baltimore • Baltimore Crisis Response- [contact] • Suicide Prevention [contact] • Columbia [contact] • Frederick [contact] • Glen Burnie (Serving Baltimore County) [contact] • Hyattsville (Serving Anne Arundel, Calvert, Charles, Montgomery, Prince George's & St. Mary's Counties) [contact] • Rockville [contact] [contact] TTY • Salisbury [contact](HELP) [contact]
Washington D C [name] (Arlington)	
 • Arlington [contact]
Virginia [name] For DC Metropolitan area http://www.suicide.org/hotlines/virginia-suicide-hotlines.html	
 • Arlington [contact] • Dumfries[contact] • Richmond [contact] • Roanoke[contact] (8:15 am to midnight) • Winchester [contact]

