If clinically important, unanticipated adverse problems or clinically important study-related, serious adverse events occur, they will be recorded on a designated case report form. All events that are serious and unanticipated, or study-related and adverse will be reported to IRB within the required reporting timeline.

Definitions:

Adverse event: any untoward medical occurrence associated with the use of a drug in humans, whether or not considered intervention related.

Serious Adverse Event (SAE) - an adverse event will be considered "serious" if, in the view of the investigator, it results in any of the following outcomes: death, a life-threatening adverse reaction, re-hospitalization, a persistent or significant incapacity, or substantial disruption of the ability to conduct normal life functions.

Suspected Adverse Event - any adverse event for which there is a reasonable possibility that the drug caused the adverse event.

Unexpected Adverse Event - an adverse event or suspected adverse reaction is considered "unexpected" if it is not listed in the investigator brochure or is not listed at the specificity or severity that has been observed; or, of an investigator brochure is not required or available, is not consistent with the risk information described in the general investigational plan or elsewhere in the current application.

d. Legal risks such as the risks that would be associated with breach of confidentiality.

All patient data will be confidential and secure due to physical and electronic data security measures, including locked offices and locked filing cabinets for records and computers, and password protection for computers and electronic data storage. All participant-identifying information will be removed from the dataset before analysis. Only study staff who are required to, will know the linkage between the unique identifier and participant-identifying information. We will keep all patient information confidential in

accordance with Public Health Services Act (42 USC 299a-1(c)). There is low risk of a breach of confidentiality.

e. Financial risks to the participants.

There are no expected financial risks to the participants.

9. Benefits

a. Description of the probable benefits for the participant and for society.

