Currently, there are few therapeutic options with proven, or potential, efficacy to prevent or minimize depressive symptoms in acute respiratory failure survivors. Hence, this study offers important new knowledge through testing the BA-R intervention in this patient population. The BA-R intervention has been demonstrated to improve depressive symptoms in other chronically ill populations. Given the prevalence of depressive symptoms in acute respiratory failure survivors, gaining information regarding the feasibility and potential benefit of BA-R in this pilot study has great importance. This therapy is especially ideal in acute respiratory failure survivors because it can be delivered via phone with only 2 home visits required by PT and OT. The potential benefits far outweigh the minimal potential risks of this intervention.

If successful, the use of BA-R therapy may improve post-acute respiratory failure depressive symptoms, improve physical function and decrease healthcare utilization while improving quality of life.

10. Payment and Remuneration

a. *Detail compensation for participants including possible total compensation, proposed bonus, and any proposed reductions or penalties for not completing the protocol.*

For each assessment during the study, both intervention and control group patients will be remunerated as follows: \$25 for baseline assessment prior to intervention period, and \$50 for assessment at the end of the intervention period.

In addition, the intervention group only will be remunerated \$100 for completion of all intervention visits.

11. Costs

a. Detail costs of study procedure(s) or drug (s) or substance(s) to participants and identify who will pay for them.

There will not be any additional costs to participants beyond routine financial obligations for their hospitalization.

References

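### IRB reporting covers every study-related adverse event but case-report-form recording is narrower, so the trial's count of minor exercise-related harms may be incomplete

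*Combined protocol and SAP*

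**What the plan says.** The paragraph on events in section 8 (Risks), directly above the Definitions list, has two consecutive sentences.

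- Recording: "If clinically important, unanticipated adverse problems or clinically important study-related, serious adverse events occur, they will be recorded on a designated case report form".
- Reporting: "All events that are serious and unanticipated, or study-related and adverse will be reported to IRB within the required reporting timeline".

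The Definitions list provides for a study without an investigator brochure. An event then counts as unexpected if it "is not consistent with the risk information described in the general investigational plan or elsewhere in the current application". The medical risks in section 8a are two. For the depression instruments: "While asking questions, we may detect that the patient has worsening depressive symptoms". For data handling: "We will be collecting data about the participant, and hence, there is a risk of breach of confidentiality". No physical harm of exercise is listed.

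Exercise is nevertheless part of BA-R. Under section 4a (Physical and Occupational Therapy Initial Home Visits), the occupational therapist sets goals "by embedding physical exercise (as recommended by PT) into valued daily routines", and the physical therapist reviews the exercise level at about six weeks. Section 9a concludes: "The potential benefits far outweigh the minimal potential risks of this intervention".

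**The concern.** One would expect whatever is reported to the IRB to be a subset of what is recorded. Here, for study-related events, it is the other way round. The form applies a test of clinical importance, and beyond that a test of seriousness or unexpectedness. The IRB limb for study-related events applies none of these.

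The events that fall between the two rules are mostly minor ones, such as a mild strain or passing exertional symptoms during recommended exercise. These are plausible harms of a home activity programme. A pilot that is meant to inform a larger trial should be able to count them. If some are known only through IRB correspondence, a low count in the trial data could reflect the recording filter as much as the intervention, and it would say little about the claim of minimal risk in section 9a.

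**Working it through.** The plan gives no figure to reproduce. The check is to write the two sentences as conditions and compare them.

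**Inputs.** Four attributes of an adverse event, all taken from the two sentences: clinically important (C), study-related (R), serious (S), unanticipated (U).

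- Recorded on the form = (C and U) or (C and R and S).
- Reported to the IRB = (S and U) or R.

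**Study-related events (R true).** The eight possible combinations are:

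| C | S | U | To IRB | On form |
|---|---|---|---|---|
| yes | yes | yes | yes | yes |
| yes | yes | no | yes | yes |
| yes | no | yes | yes | yes |
| yes | no | no | yes | **no** |
| no | yes | yes | yes | **no** |
| no | yes | no | yes | **no** |
| no | no | yes | yes | **no** |
| no | no | no | yes | **no** |

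All eight go to the IRB and three go on the form. The five that do not are the four that are not clinically important and the one that is clinically important, non-serious and anticipated. These rows show where the rules diverge. They are not equally likely, so the count does not measure the size of the problem.

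**Which rows matter in practice.**

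1. Two of the five are serious but not clinically important. The Definitions list makes an event serious through outcomes such as death, threat to life, re-hospitalization or lasting incapacity, so these rows are practically empty. Three remain, all non-serious.
2. Section 8a lists no exercise harm. If *unanticipated* in the recording rule means the same as the defined *unexpected*, an exercise harm is ordinarily unanticipated. The two anticipated rows are then empty for exercise, and one row remains: study-related, non-serious, unanticipated and not clinically important.
3. The protocol does not equate the two terms. If section 8a were amended to list exercise harms, such harms would become anticipated, and the non-serious ones would leave the recording rule even when clinically important.

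**Other routes into the data.**

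- Table 4 has no adverse-event outcome.
- The healthcare utilization data (section 7b, Table 2) cover facility admissions and mental health and rehabilitation services. A strain treated at home need not appear there.
- The therapist calls (section 4a) ask about goals and barriers to adherence.
- The adherence measures (section 7b) count call attempts and completed sessions.
- The serious-event form in section 8b belongs to the suicide-risk procedure.
- Section 7c describes no harms summary.

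**Alternative reading of the IRB sentence.** If *serious* governed both limbs, reported = S and (U or R). The only events then reported but not recorded would be serious ones that are not clinically important, which are practically empty. The mismatch would all but vanish. The recording rule would still omit non-serious study-related events that are anticipated or not judged clinically important.

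**The case against.** The strongest reply is that the gap is narrow and concerns events that matter least. A clinically important fall or strain that was not anticipated goes on the form whether or not it is serious. A disabling study-related injury would probably meet the definition of serious through its limb on disrupted normal life. What is left is minor events, and a single-site behavioural pilot whose outcomes do not include safety may reasonably choose not to log them. This stands as a limit on importance. It does not explain why events the plan already requires to be reported should have no stated place in the trial data.

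A reader might infer that non-serious harms of the exercise programme never reach the trial data. The documents do not support that:

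- The form takes clinically important, unanticipated, non-serious problems.
- The recording sentence says what goes on one designated form. It does not say that nothing else is kept.
- The part of section 8 between the helpline table in 8b and this paragraph is not in the text available to this review, so absence from the whole plan cannot be shown.

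A reader might also want to say how many patients would be missed. No event rate appears anywhere in the documents, so any such number would be invented.

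Finally, the section 9a statement is a benefit-risk judgement and not a trial hypothesis. Leaving it untested defeats no stated aim, though it remains a question that a later trial would ask.

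**Conclusion.** The point holds in a limited form. On the plain reading of the IRB sentence, study-related events that are not judged clinically important, or are non-serious and anticipated, are reportable with no stated requirement in the available text to record them as trial data. The count of minor exercise-related harms may therefore be incomplete, and no summary of harms is planned in that text.

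The size in patients cannot be given. In kind, the gap for exercise comes down to non-serious events judged not clinically important if *unanticipated* equals *unexpected* and section 8a stays as it is. It is wider if either condition fails. The visible text does not define *clinically important*, so the boundary depends on the assessor's judgement.

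Neither the feasibility outcomes nor the efficacy analyses are affected. This is a worthwhile and inexpensive correction, not a flaw that threatens the trial's aims.

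**What to change.** Align the two sentences in section 8: every study-related adverse event that is reportable to the IRB is also recorded on the case report form, whether or not it is serious, anticipated or judged clinically important, with its date, severity and the activity involved. If the sponsor meant *serious* to govern both limbs of the IRB sentence, it should say so and still widen the recording sentence.

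Add one line to section 7c: report descriptively, beside the feasibility results, the number of BA-R patients with at least one study-related adverse event, with an exact (Clopper-Pearson) 95% confidence interval. To show the precision on offer, with 0 events in 27 patients the upper limit would be 1 − 0.025^(1/27) = 12.8%. No between-arm test is needed.

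The definitions of adverse event and suspected adverse event are written for a drug ("any untoward medical occurrence associated with the use of a drug in humans, whether or not considered intervention related"), while section 6 is marked not applicable. They should be reworded in the same amendment, but that alone would leave the recording filter in place.

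The cost is a small amendment and one form entry, completed from contacts the therapists already make (nine scheduled calls plus the visits). The downside is a few more minor events to document in about 27 BA-R patients, or 32 if all 10 additional patients are enrolled and split evenly: (54 + 10)/2 = 32.
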